14.3. Early Termination of the Study

The Sponsor may discontinue the study at any time.

If, in the opinion of the investigator, the clinical observations in the study suggest that it might not be justifiable for medical reasons to continue, she/he may terminate the study after consultation with the Sponsor or the Sponsor may terminate the trial for safety, administrative or other reasons.

Reasons for discontinuation have to be documented appropriately and to be provided to the Sponsor and the Ethics Committee and MoH. In case of premature discontinuation of the study a complete final examination has to be performed for each volunteer as far as possible with regard to the volunteer's health conditions and as far as necessary with regard to safety aspects and the validity of study results.

14.4. Drop-out Samples

All drop-out samples which will be sent by the clinic will be analysed and results will be given in the Final Study Report.

15. ADVERSE EVENTS

15.1. Definition of Adverse Event / Serious Adverse Event / Adverse Drug Reaction / Unexpected Adverse Drug Reaction

An Adverse Event (AE) is any untoward medical occurrence in a patient or clinical investigation subject administered a pharmaceutical product which does not necessarily have a causal relationship with this treatment.

An AE can therefore be any unfavourable and unintended sign (including an abnormal laboratory finding, for example), symptom, or disease temporally associated with the use of a medical product, whether or not considered related to the medical product.

A Serious Adverse Event (SAE) is any untoward medical occurrence that at any dose:

- results in death
- _ is life-threatening
- results in persistent or significant disabling/incapacity
- requires inpatient hospitalization
- prolongs inpatient hospitalization
- is a congenital anomaly/birth defect

An adverse event is defined as an **Adverse Drug Reaction (ADR)** if further analyses prove that the adverse event was caused or partially caused by the study medication:

In the pre-approval clinical experience with a new medicinal product or its new usage all noxious and unintended responses to a medicinal product related to any dose should be considered adverse drug reaction. The phrase "responses to a medicinal product" means that a causal relationship between a medicinal product and an adverse event is at least a reasonable possibility, i.e. the relationship cannot be ruled out.

Unexpected Adverse Drug Reaction (UADR) is an adverse reaction, the nature or severity of which is not consistent with applicable product information (e.g., Investigator's Brochure for an unapproved experimental medicinal product, summary of product characteristics for an approved product) or events previously unobserved or undocumented which are not on the basis of what might be anticipated from the pharmacological properties of a medicinal product.

In the course of the study, the investigator will determine whether any adverse events have occurred and will grade their intensity as follows:

- Mild: Awareness of symptoms but easily tolerated

- Moderate: Discomfort enough to cause interference with usual activity

- Severe: Incapacitating with inability to work or to carry out usual activity.

15.2. Relationship to the Study Medication

The investigator will make judgement considering whether or not, in his opinion, the adverse event was related to the drug according to the following classification. However, even if the investigator feels that there is no relationship to the drug, the adverse event should be reported.

The likelihood of the relationship of adverse event to the study drug is to be recorded as follows.

Causality assessment of suspected adverse reactions (criteria defined by members of WHO Drug Monitoring Programme):

- Certain: A clinical event, including laboratory test abnormality, which occurs in a plausible time relationship to drug administration, and which cannot be explained by concurrent disease or other drugs or chemicals. The response to withdrawal of the drug (de-challenge) should be clinically plausible. The event must be definitely pharmacological or phenomenological, using a satisfactory re-challenge procedure if necessary.
- Probable/likely: A clinical event, including laboratory test abnormality, with a reasonable time sequence to administration of the drug, unlikely to be attributed to concurrent disease or other drugs or chemicals, and on which a clinically reasonable response on withdrawal (de-challenge) follows. Rechallenge information is not required to fulfil this definition.
- Possible: A clinical event, including laboratory test abnormality, with a reasonable time sequence to administration of the drug, but which could also be explained by concurrent disease or other drugs or chemicals. Information on drug withdrawal may be lacking or unclear.
- Unlikely: A clinical event, including laboratory test abnormality, with a temporal relationship to drug administration which makes a causal relationship improbable, and in which other drugs, chemicals or underlying disease provide plausible explanation.
- Conditional/unclassified: A clinical event, including laboratory test abnormality, reported as an adverse reaction, about which more data is essential for a proper assessment or the additional data are under examination.
- Unassessable/unclassified: A report suggesting an adverse reaction which cannot be judged because information is insufficient or contradictory, and which cannot be supplemented or verified.

Study Code: NOV2020/01917
Clinical Study Protocol
Version: 1.0

15.3. Reporting and Documentation of Adverse Event(s)

AEs/ADR will be assessed by spontaneous, unsolicited reports of the volunteers, by observation and by routine open questionings of the volunteers. Questionings will be done by experienced staff of FARMAGEN-Good Clinical Practice and Research Center during admission to the clinical facility and at least at the following times of the study period: at **Day 0**, **pre dose and t**_{1.00}, **t**_{4.00}, **t**_{8.00}, **t**_{14.00}, **t**_{24.00} hours after the drug administration. If any adverse event occurs, it will be recorded on the Adverse Event Report page of the CRF. All findings will be recorded in English. The documentation includes type of AE/ADR, date and time of onset, treatment initiated (if applicable), outcome, intensity/severity code (mild, moderate, severe) and whether the event is serious. It is important that the investigator immediately reports any adverse event which by the definitions given above would be considered serious, even if the investigator does not consider the adverse event to be clinically significant or drugrelated.

Occurrence of any serious adverse event has to be reported by the investigator immediately (within 24 hours), the latest on the next working day, by phone and email and/or by fax to **Atabay Kimya San. ve Tic. A.Ş. or to ALPAN FARMA** as an initial report.

As soon as new information about the SAE becomes known, the investigator has to forward it without any delay to **Atabay Kimya San. ve Tic. A.Ş. or to ALPAN FARMA**. This applies to the follow-up and/or final SAE report and all medical records associated with it.

A copy of the updated CRF-page for AE and SAE documentation will be forwarded to **ALPAN FARMA or Atabay Kimya San. ve Tic. A.Ş.** as soon as possible.

The responsible sites for the upper procedure are:

Atabay Kimya San. ve Tic. A.Ş.	Alpan Farma Ltd.Şti.
Contact Person	Contact Person
[name], Chem.	[name]. [name]
Phone: ([contact]	[contact]
[contact]	GSM: [contact]
GSM: [contact]	E-mail: [contact]
E-mail: [contact]	

Serious adverse events will be reported to sponsor and/or CRO by investigator immediately. After that, sponsor and/or CRO will report to the EC, MoH and to the regulatory authorities of the study site according to the local legal requirements in 7 days.

Serious Adverse Events which occurred within two weeks after termination of the clinical trial and which are considered to be related to the trial must also be reported.

Any Adverse Event which is not resolved at the final visit should be followed-up until it will be resolved or assessed as a stable condition or causality other than the trial medication has been found.

16. STUDY DOCUMENTATION

16.1. Investigator's File

The investigator Trial File of the study will be included at least the following documents:

- 1. Investigator and co-investigator's curriculum vitae
- 2. Correspondence including relevant notes from telephone contacts
- 3. List of monitoring visits/audit visits/inspections
- 4. Signature sheet of clinical team
- 5. Final volunteer information and informed consent form and volunteer identification
 - 5.1 Signed informed consent forms
 - 5.2 Sample Volunteer information and informed consent with any translation
 - 5.3 Volunteer identification (screening log, identification list)
- 6. Test and Reference Products
 - 6.1 Drug accountability sheets (receipt, dispense, return)
 - 6.2 Shipment, receipt, return, etc.
 - 6.3 Sample of labels attached to investigational product(s) containers
- 7. Investigational products accountability at the site
- 8. Trial Material (orders, deliveries, shipments, return and disposal if applicable)
- 9. Study Protocol
- 10. Special instructions concerning the conduct of the study, if available
- 11. Sample CRF book
- 12. Analytical Study Plan
- 13.Hematology, Biochemistry and Serology tests' normal ranges and certification/accreditation of Test's Laboratory
- 14. Safety Documentation
 - 14.1 Documentation of SAE reports
 - 14.2 Safety overviews: periodic reports sent to EC and MoH (country specific/whole study)
 - 14.3 Erroneous SAE reports
- 15. EC and MoH approval
- 16. Insurance statement and conditions
- 17. Subject screening and enrolment log
- 18. Subject identification code list
- 19. Regulatory Authority Approval/Notification (if applicable for the centre)
- 20. GCP statement of investigator, personnel responsibilities signatures and CVs
- 21. Financial arrangements and contracts with sponsor/investigator/CRO
- 22. Product information (Investigator' Brochure or Summary of Product Characteristics)
- 23. ICH-GCP Guidelines and local law (if applicable)
- 24. CRFs of volunteers screened but not randomised (copies)
- 25. CRFs of volunteers enrolled in the study in ascending order (copies), source Documents
- 26. According to ICG GCP a copy of site initiation report should be added in Investigator's site File

16.2. Case Report Form (CRF)

NOVAGENIX will design the Case Report Form in close co-operation with the Sponsor. Standardized CRFs will be used as **source document regarding** volunteers' raw data during the course of the study. The investigator will assure that all data are entered promptly, legibly, completely, accurately and in accordance with other source documents (e.g. ECGs, laboratory results, diet and fluid intake records). This procedure will be applied to the data of both volunteers who met the inclusion criterion and will be included into the study and the volunteers that will not be included into the study because of a valid reason.

To ensure legibility, the CRFs should be filled out only with a blue ball-point.

Any corrections to the CRFs must be carried out by the investigator or his designate. A single stroke must be drawn through the original entry. The reason for the correction has to be given and it has to be dated and initialled. Incorrect entries must not be covered with correcting fluid, or obliterated, or made illegible in any way.

Even if there are no changes from a previous examination, in the interests of completeness of data acquisition, the questions which are repeated in each section of the CRFs should be answered in full text. A reasonable explanation must be given by the investigator for all missing data.

The CRFs will be completed immediately after termination of the individual treatment and observation periods and the final examination. After being signed by the investigator, they will be sent to NOVAGENIX for data validation. Thereafter, CRFs will be returned to NOVAGENIX and eventually forwarded to the Investigator for final corrections, if applicable. CRFs can not be sent by post but only be personally submitted to the NOVAGENIX monitor during a visit or sent by courier. Any other way of transport is to be previously discussed with the NOVAGENIX. NOVAGENIX will send the original CRFs to Sponsor with the final report of the study. NOVAGENIX will store the copy of all CRFs.

All medical records upon which the CRFs are based must be kept for at least 14 years after completion of the study. At this time ALPAN Farma will discuss with the Sponsor whether or not storage is required for a longer period. Image carriers or other data carriers can be used for the purpose of storage.

17. ANALYTICAL EVALUATION

Plasma concentrations of **favipiravir** will be determined by means of a validated **LC** method, according to Novagenix's SOP NOV-ENG-08-TEC1.

Detailed characteristics of the analytical method applied will be described in the "Analytical Study Plan" (see **Appendix III: Analytical Study Plan**). All assay validations will be performed in consideration of the Guideline on Bioanalytical Method Validation, EMA, 21 July 2011 and US FDA Guidance for Industry, Bionalytical Method Validation May 2018 or current guidance on method validation date.

Volunteer's all samples will be measured in a single analytical run in order to eliminate the influence of the inter-assay variance on the assessment. The analyst has to provide a final analytical report with tables for all samples that were analysed.

Already measured samples will be stored at <-20°C for at least 6 months (storage period can be prolonged in exceptional cases, e.g. upon special request of authorities) after termination of bio-analysis. At that point a further decision by the Sponsor will be taken.

20% of the chromatograms are to be included in printed Final Study Report. But 100 % of chromatograms will be given also as electronically.

17.1. Reanalysis of study samples

The reasons for reanalysis of study samples are presented in **Appendix III: Analytical Study Plan.**

17.2. Incurred Sample Reanalysis

Incurred Sample Reanalysis (ISR) will be performed at any time after starting subject analysis by choosing two sampling points near or at C_{max} and two sampling points in the elimination phase per period (total 8 sampling points per subject). These ISR points will be selected according to the literatures and/or in the very first batches of subject analysis. The subjects will be randomly selected and the number of subjects that defined as ISR points will be equal or more than 10% of samples for the first 1000 study samples and an additional 5% of samples for study samples in excess of 1000. The difference between the study samples' and incurred samples' values obtained should be within 20% of the mean for at least 67% of the repeats according to EMEA/CHMP/EWP/192217/2009 Rev.1 Corr.2. Guideline on Bioanalytical Method Validation. London, 21 July 2011, p.13-14; Novagenix's SOP-NOV-ENG-08-CQU4 and documented in the Final Study Report.

18. PHARMACOKINETIC EVALUATION

Pharmacokinetic parameters of **favipiravir** will be determined using non-compartmental methods from measured plasma concentrations.

For each treatment (**Test Drug** or **Reference Drug**) and each volunteer participating completely in this **single-dose**, **two period**, **cross-over study** the following pharmacokinetic parameters will be calculated:

Primary pharmacokinetic parameters:

C_{max}: Maximum observed plasma concentration

AUC_{0-tlast}: Area under the plasma concentration-time curve from zero to the last measurable concentration, calculated by the linear log trapezoidal rule.

Secondary pharmacokinetic parameters:

 $AUC_{0-\infty}$: Area under the plasma concentration-time curve, calculated by extrapolation to infinity.

 t_{max} : Time to maximum observed plasma concentration

 $t_{1/2}$: Terminal half-life

Additional pharmacokinetic parameters:

MRT: Mean residence time

 λ_z : Terminal rate constant.

For pharmacokinetic calculations, the program package **Phoenix WinNonlin (Version 8.1, Certara L.P.)** or above will be employed. Phoenix WinNonlin will also be used to generate concentration/time plots.

19. STATISTICAL PROCEDURES

The statistical analysis of the pharmacokinetic data described in this section corresponds with provisions according to the *EMA guideline for bioequivalence (Doc. Ref.: CPMP/EWP/QWP/1401/98 Rev. 1/ Corr* **)- 2010.

Statistical analysis will be performed as a valid case analysis including all volunteers in which no major protocol deviations occurred and all primary target variables are available for measurement.

If a volunteer is to be excluded from evaluation, this decision has to be justified in the Final Study Report. Statistical analysis will be performed by means of the program **Phoenix WinNonlin (Version 8.1, Certara L.P.)** or above.

19.1. Target Variables

19.1.1. Primary Target Variables

C_{max} and AUC_{0-tlast} are declared to be primary target variables.

19.1.2. Secondary Target Variables

 $AUC_{0-\infty}$, t_{max} and $t_{1/2}$ are declared to be secondary target variables. MRT and λ_z will be determined also.

In order to achieve a better approximation to a normal distribution C_{max} and AUCs data will be logarithmically transformed (base e) before analysis. The sources of variation will be treatments, periods, sequence and subjects (nested within sequence) in Analysis of variance (ANOVA). Evaluation of treatment, period, sequence and subject (nested within sequence) effects at 5% level of significance will be performed. From the result of this procedure, the two one-sided hypothesis at the 5% level of significance will be tested by constructing the 90% confidence interval for the geometric mean ratios test/reference products. The confidence interval is calculated by retransformation of the shortest confidence interval for the difference of the Intransformed mean values. Differences in t_{max} will be evaluated non-parametrically.

Bioequivalence will be concluded if the 90% confidence intervals for the geometric mean ratios of the products (test/reference) are fully contained within the limits of acceptance of 80% - 125% for C_{max} and $AUC_{0-tlast}$. For the secondary target variables, the 90% confidence intervals will be investigated for exploratory purposes.

Evaluating excluding values from statistical calculations, the criteria which are given in "Novagenix SOP-NOV-ENG-08-CQU5" will be applied.

These criteria are;

- 1. If a suspicious case about safety of blood samples such as in the absence of label, label is not read exactly or any confusion of sample, these samples are documented on "Protocol For Handing Over Receipt of Samples" form. These samples are analysed but not included in statistics.
- 2. After completing study analysis, reanalysis is done due to analytical reason according to SOP-NOV-ENG-08-TEC1 and SOP-NOV-ENG-08-CQU4. If the reanalysed data is still invalid for the analytical reason and there is insufficient plasma sample for reanalysis, that data should be excluded from statistical analyses. Any exclusion should be properly reported on final study report.

3. A subject with lack of any measurable concentrations or only very low plasma concentrations for reference medicinal product. A subject is considered to have very low plasma concentrations if its AUC is less than 5% of reference medicinal product geometric mean AUC (which should be calculated without inclusion of data from the outlying subject). That subject will be evaluated and may be excluded. Accordingly the two results are reported in final study report.

- 4. Subjects with non-zero baseline concentrations > 5% of C_{max} . Such subject should be excluded from statistical calculation.
- 5. Total number of subject should not be under 12 in the statistical calculation, whether not this study would be repeated from the clinic part.

19.1.3. Safety Evaluation

The assessment of safety will be based mainly on the frequency of AEs and on the number of laboratory values that fall outside of pre-determined ranges. Other safety data (e.g. electrocardiogram, vital signs and special tests) will be considered as appropriate.

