11. SELECTION OF VOLUNTEERS

11.1. Inclusion Criteria

Only volunteers fulfilling all of the following criteria should be enrolled in the present trial:

- 1. Healthy Caucasian male subjects aged between 20 and 40 years,
- 2. Non smokers or smoking maximum 5 cigarettes a day, those who won't smoke or drink coffee during the study period,
- 3. Two Negative Covid-19 PCR test# results.
- 4. Negative alcohol breath test results,
- 5. Normal physical examination at screening visit,
- 6. Having the Body Mass Index ranged between 18.5-30 kg/m² (see Appendix I) which is in the desirable range according to the age,
- 7. Ability to communicate adequately with the investigator himself or his representatives,
- 8. Ability and agreement to comply with the study requirements,
- 9. Normal blood pressure and heart rate measured under stabilised conditions at the screening visit after at least 5 minutes of rest under supine position: SBP within 100 to 140 mmHg, DBP within 60 to 90 mmHg and HR within 50 to 90 bpm,
- 10. Normal/acceptable 12-lead electrocardiographic results at least after 5 minutes of rest,
- 11. Laboratory results within normal range or clinically non-significant (CBC, glucose, urea, uric acid*, creatinine, estimated GFR (eGFR), total bilirubin, sodium, potassium, calcium, chloride, SGOT (AST)*, SGPT (ALT)*, GGT*, alkaline phosphatase, total protein and urinalysis), drug addiction scanning in urine results in negative (amphetamine, barbiturate, benzodiazepine, cannabinoid, cocaine, opiate),
 - * SGOT (AST), SGPT (ALT), GGT and uric acid levels should be within normal range.
- 12. Understanding of the study and agreement to give a written informed consent according to section 20.3.
- 13. Understanding of that he and his partner will use a practice adequate contraception during the study and at least 7 days after the study.

 $^{\#}$ One of the Covid-19 PCR test will be applied on examination day, the other will be applied on the 5^{th} isolation day

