At screening volunteers will be requested to provide a urine sample for a drug screen which will include "amphetamines, cannabinoids, benzodiazepines, cocaine, opioids and barbiturates" and for an alcohol breath test. All laboratory tests will be carried out in a certified local laboratory. A list of the normal ranges and units of measurement of the laboratory parameters to be determined during the study and the certificate of the laboratory will be provided by the investigator before the start of the study. The reference ranges and the results of the individual laboratory examination will be documented in each CRF. The investigator will be provided with a print-out or authorized copy of the original laboratory values.

If in the course of initial screening any clearly pathological value (laboratory value outside reference range, clinically relevant or significant) is observed, this finding will be regarded as an exclusion criterion.

Laboratory values outside the normal range will be judged by the investigator in a written form in the CRF. Single laboratory values outside the normal range will generally not be regarded as an exclusion criterion provided that:

- a) they are not accompanied by clinical symptoms,
- b) the context of related laboratory values gives no indication of a pathological process and
- c) the investigator regards them as clinically irrelevant in written form in the CRF.

If any positive result in Covid-19 PCR test is observed, the volunteer will be transfer to Gaziantep University Şahinbey Research Hospital, Emergency Department* under appropriate conditions immediately. This finding will be regarded as an exclusion criterion.

*Contact Physician: [name]. [name]

Gaziantep University Şahinbey Research Hospital, Emergency Department

GSM: [name]

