The test and reference product will be administered under fasting conditions each in a randomised manner in two-period with at least 48 hours wash-out period. Volunteers will be treated under hospitalization conditions in study period and will be hospitalised at the Clinical Facility (FARMAGEN-Good Clinical Practice and Research Center) from the evening of Day 0 (hospitalization day) normally until taking the last blood sample in 2nd period and carried out the post-study and final examination to ensure subjects' safety as well as standardised trial conditions during profiling days (e.g. in view of food and fluid intake, diet, fasting conditions, drug administration, clinical and other procedures). Adverse events will be monitored throughout the study. The medical care of the volunteers will be guaranteed by the presence or stand-by of the investigator or one of the co-investigators throughout the clinical phase of this trial.

The volunteers will come to the clinic from isolation, described at Appendix VII, at approximately **18:00** on the day before the treatment (Day 0) and will remain there for **90 hours**. A measurement of body temperature will be performed once a day in the mornings during the study period. They will not be allowed to drink water between 1 h before to 1 h after administration, except while dosing (the total intake of water on the days of dosing will be maximum 1.5 L). The investigator will check on each volunteer's wellbeing prior to their discharge from the clinic. If necessary, some volunteers will remain at the clinic until any adverse events have resolved. All volunteers will be subjected to a post-study and final examination and laboratory tests on the day of last sampling in **second period**.

For each volunteer being withdrawn from the study prior to regular termination of the individual study period, due to whatever reason, a complete final examination has to be performed at the time of withdrawal as far as possible with regard to the volunteer's health conditions and as far as necessary with regard to safety aspects. All taken

plasma samples will be analysed. But will not be included to statistical calculations.

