- Blood sampling (0.17-24.00 hours) will be done after drug administration with separation of plasma
- Standardised lunch will be served at 4 hours after the dosing (between 12:00 p.m. to 13:00 p.m.)
- Standardised dinner will be served at 10 hours after the dosing (between 18:00 p.m. to 19:00 p.m.)
- Standardised light breakfast will be served at approximately 21.30 pm.
- Questioning for and registration of adverse events at hospitalisation day (Day 0), pre dose and 1.00, 4.00, 8.00, 14.00, 24.00 hours post-dose*.
- Standardised breakfast and lunch will be served on day 4.
- Discharge from the clinic (after final examinations)

Final examination:

- The final examination will be carried out on the day of last blood sampling of the 2nd **period**. The following parameters will be documented: Interview (occurrence of adverse events)
- Clinical screening and examination (clinical state: body temperature, BP, PR, ECG, registration of pathological findings, if any, clinical chemistry, Covid-19 PCR test, haematology, urinalysis)
- Laboratory screening. The sampling for laboratory screening can be performed together with the last sampling for the kinetic profile in **24 hours** post-dose. Abnormal laboratory findings which are judged by the investigator as adverse event at the final examination should be followed up until it will be resolved or is assessed as stable condition or a causality other than trial medication was found and whole data that collected during the entry examination, study period and final examination will be documented in the CRF.

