13.8. Endpoint(s) For The Study

Primary Endpoint: AUC_{0-tlast} and C_{max} of **favipiravir**

Secondary Endpoint: AUC_{0- ∞}, $t_{1/2}$, t_{max} of **favipiravir**

Safety Endpoints: Adverse events, clinical and laboratory examinations.

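### The laboratory safety measure is a raw count of out-of-range values that ignores the entry value, so tolerated entry abnormalities are counted as findings and within-range falls are missed

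*Combined protocol and SAP*

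**What the plan says.** Laboratory examinations are a named safety endpoint: Section 13.8 lists "Adverse events, clinical and laboratory examinations". Section 19.1.3 says how they will be assessed. Alongside the frequency of adverse events, the main basis is "the number of laboratory values that fall outside of pre-determined ranges". It does not mention the entry value, change, shift or treatment-emergent status, and it does not say which examination is counted. Section 19.4 adds a descriptive analysis of the safety data in the CRFs, without further detail.

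Entry is permissive for most analytes. Section 11.1 admits volunteers with "Laboratory results within normal range or clinically non-significant", with one exception: "SGOT (AST), SGPT (ALT), GGT and uric acid levels should be within normal range". Section 13.1 adds that "Single laboratory values outside the normal range will generally not be regarded as an exclusion criterion provided that" three conditions are met: no accompanying symptoms, no sign of a pathological process in related values, and a written judgement of clinical irrelevance.

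The flow chart in Section 6 schedules the chemistry, haematology and urine panel twice, at screening and at the final examination. On the second, Section 13.1 says "All volunteers will be subjected to a post-study and final examination and laboratory tests on the day of last sampling" of the second period, and Section 13.3 says "The sampling for laboratory screening can be performed together with the last sampling for the kinetic profile".

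**The concern.** A count of values outside a range answers a safety question only if the values were inside that range before dosing. The entry criteria guarantee this for four analytes and deliberately do not for the rest. The count can then mislead in two directions.

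- **Upward.** A volunteer admitted with a tolerated abnormality that has not changed by the final examination adds to the count, although nothing happened on study.
- **Downward.** A volunteer whose value drops markedly but stays within range adds nothing. Section 7.6 lists decreased neutrophil count and decreased white cell count among reactions at 1% or more. Both belong to the CBC, which has no strict entry rule.

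What is at stake is how readable the laboratory safety summary is, for a product whose listed reactions include laboratory changes.

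**Working it through.** The plan gives no figure for this measure, so there is nothing to reproduce. The point rests on setting the sections side by side; the arithmetic only illustrates it.

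**Step 1: which analytes may be out of range at entry.** Section 11.1 names 15 chemistry items: glucose, urea, uric acid, creatinine, eGFR, total bilirubin, sodium, potassium, calcium, chloride, AST, ALT, GGT, alkaline phosphatase and total protein. With CBC and urinalysis there are 15 + 2 = 17 items. Four must be normal. That leaves 15 − 4 = 11 chemistry items, or 17 − 4 = 13 items in all, that may be out of range at entry.

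**Step 2: how the count treats each pattern.**

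| Entry | Final | Counted at final? | Informative about the study? |
|---|---|---|---|
| In range | Out of range | Yes | Yes, apart from chance |
| Out of range, tolerated | Out of range, unchanged | Yes | No |
| Out of range, tolerated | Out of range, worse | Yes, but looks the same as unchanged | Yes |
| In range | Lower, still in range | No | Possibly |

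The count merges the first three rows and omits the fourth. Separating them needs only the entry value, which is already recorded in the CRF.

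**Step 3: which product the panel follows.** For a volunteer who completes both periods, the only scheduled post-dose panel comes after both Test and Reference. Referring to entry does not change that, so the result describes the sequence of two products. Under Sections 13.1 and 14.2 a volunteer who withdraws has the final examination at withdrawal, which may follow one product only.

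**Step 4: illustration of size.** The following are assumptions that the documents do not state: each range covers 95% of healthy values (p = 0.05), there is no drug effect, entry and final values are bivariate normal with correlation ρ, and selection at entry does not lower the rate.

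Expected out-of-range values at final = volunteers × analytes × p = 30 × 11 × 0.05 = 16.5. At p = 0.025 this is 30 × 11 × 0.025 = 8.25.

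Share already out at entry = P(out at both) / p. For p = 0.05:

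| ρ | Share already out at entry | Newly out of range, of 16.5 |
|---|---|---|
| 0 | 5% | 15.7 |
| 0.5 | 19% | 13.4 |
| 0.7 | 33% | 11.0 |
| 0.9 | 59% | 6.7 |

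Referring to entry removes the pre-existing part. The values in the last column are chance excursions and remain, so change from entry is needed as well as a count of newly out-of-range values.

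**The case against.** The best case for the plan has four parts.

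1. **No decision rests on the count.** Bioequivalence is concluded from Cmax and AUC0-tlast alone, and no threshold or test is attached to the laboratory count. This stands, and it limits the point to the quality of the safety report.
2. **Clinical judgement screens the values.** Section 13.1 says "Laboratory values outside the normal range will be judged by the investigator in a written form in the CRF". Section 15.1 lets an abnormal laboratory finding be an adverse event, and Section 13.3 has final findings judged to be adverse events followed up. An abnormality that emerges on study and is so judged therefore reaches the adverse event frequency. This also stands, but the judgement is not linked to the laboratory count, which Section 19.1.3 treats as a separate basis.
3. **The entry tolerance is narrow.** Section 13.1 speaks of single values and sets three conditions, and clearly pathological values exclude. Fewer abnormalities may therefore be carried in than an unselected 5% rate implies. This weakens the illustration, not the definition.
4. **The ranges are undefined.** Section 19.1.3 does not say what its ranges are. Section 13.1 has the laboratory's normal ranges supplied before the start, so those are the natural reading. Any fixed range has the same defect if entry is ignored.

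A reader might go further and infer that the count will be taken as a comparison of Test with Reference, or that blood loss will drive the haematology results. The documents support neither. Section 19.1.3 proposes no comparison between products. Section 13.7 gives about 358 mL in total, which leaves 358 − 12 = 346 mL without the final safety sample, but no document gives the effect of that volume on any laboratory value.

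**Conclusion.** The point holds as a matter of definition. As written, the laboratory measure counts tolerated entry abnormalities that persist, cannot tell an unchanged one from a worsened one, and does not see a change that stays within range. Thirteen of the 17 listed laboratory items are exposed to the first two problems; the third applies to every numeric analyte, including the four restricted at entry.

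The size cannot be fixed from the documents. The 16.5 expected values, and the 5% to 59% of them removed by referring to entry, depend wholly on the assumed rate and correlation. A reader might infer from the upper end that most of the count will be carried over from entry. The documents do not support that: they give no correlation, and at 0 to 0.5 the share is only 5% to 19%.

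The bioequivalence conclusion is unaffected, and adverse event frequency remains a separate route for abnormalities judged to matter. This is an inexpensive improvement that should be made, not a flaw that undermines the trial.

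**What to change.** In Section 19.1.3, replace the raw count with the following.

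- An entry-to-final shift table (low, normal, high) for every analyte, using the laboratory's normal ranges; for urine strip results, normal and abnormal.
- Values newly out of range at final, reported separately from those already out of range at entry.
- A flag for entry abnormalities that worsened, meaning that they moved further from the range limit. A table of categories alone would show these as no shift.
- Descriptive change from entry for all numeric analytes, including AST, ALT, GGT, uric acid, neutrophils and white cells.
- A statement that the only scheduled post-dose panel follows both products, so that laboratory findings describe the two-product sequence and are not attributed to Test or Reference. Volunteers withdrawn after one period should be listed separately with the product received.

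The cost is one table and a few sentences. Entry and final results are already collected and recorded in the CRF, so no new samples or visits are needed.
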